#### 4.6.4 Treatment Compliance

Weight of the IP applied will be measured for reporting purposes. IP cans will be weighed at each follow-up clinic visit. The weight of the IP can will be collected prior to the IP application and after the IP application at Baseline, Weeks 2, and 4. Weight of the IP applied, and the IP cans will be recorded in the source notes and in the eCRF.

Subjects will complete a daily diary recording the date and time of each dose applied, any missed doses, and a comment section should the subjects have a comment, e.g., record potential AEs. Site personnel will review the diaries at each clinic visit and use the information to question the subject regarding compliance and AEs and then record appropriate information in source documents and complete Case Report Forms (CRFs). If a subject misses a dose, they should be instructed to return to the protocol IP administration schedule (i.e. if subject forgets a dose they should wait until that evening and apply as usual).

A subject will be considered compliant with the dosing regimen if the subject applies at least 80% of the expected applications during the IP application period and does not miss more than 3 consecutive doses.

Compliance will be assessed by review of the dosing diary. If the diary shows less than 80% of expected use, the subject is using too little IP and retraining must be conducted and documented.

Compliance will be documented in source and in eCRF.

## 5 STUDY PROCEDURES

### 5.1 Safety Assessments

The Schedule of Visits and Assessments ([Section 1.3](#)) summarizes the clinical procedures to be performed at each visit. Individual clinical procedures are described in detail below. Additional evaluations/testing may be deemed necessary by the PI and/or the Sponsor for reasons related to subject safety.

This study assesses the safety and efficacy of ARQ-154 foam 0.3%. Safety will be determined by evaluating physical examinations, local tolerability assessments, vital signs/weight, clinical laboratory parameters, PHQ-8 (adults)/modified PHQ-A (adolescents), C-SSRS and AEs as outlined in the Schedule of Visits and Assessments ([Section 1.3](#)). If deemed necessary, additional safety assessments will be performed at the discretion of the Investigator.

#### 5.1.1 Screening

Within 4 weeks prior to the first dosing (Baseline visit), subjects will be provided details of study requirements and sign an informed consent. Medical history and demographic data including sex, age, race, ethnicity, body weight (kg), and height (cm) will be recorded. Each subject will undergo psoriatic plaque assessments, a physical examination, vital sign measurements (blood pressure, heart rate, and temperature), PHQ-8 (adults)/modified PHQ-A (adolescents), C-SSRS, and laboratory tests: hematology, chemistry, urinalysis and serum (Screening) and urine (Baseline) pregnancy tests for female subjects of child bearing potential.

All screened subjects will receive a screening number and be entered into the electronic subject tracking system. Subjects may be re-screened one time, the original assigned Subject ID will be used for re-screening.

### **5.1.2 Baseline**

Randomization will take place at the Baseline visit (Day 0) after the subject has been found to be fully eligible for participation. The subject is considered enrolled into the study once randomization occurs and the subject has been assigned to one of the treatment groups.

If the Baseline visit occurs within 14 days of Screening, the Screening lab results may be utilized.

### **5.1.3 Physical Examination**

Physical examinations will be performed according to the Schedule of Visits and Assessments ([Section 1.3](#)):

Screening, Baseline and Week 8.

The physical exam will be limited to skin, lungs and heart only. System driven physical examination will be conducted in case of symptoms and adverse events.

### **5.1.4 Vital Signs, Height and Weight**

Vital signs will be collected according to the Schedule of Visits and Assessments ([Section 1.3](#)):

Blood pressure, heart rate, and temperature will be measured at Screening, Baseline, Weeks 2, 4, 8, and 9.

Height will be collected at Baseline and Week 8.

Weight will be collected at Screening, Baseline, Weeks 2, 4, 8, and 9. Subject to void prior to weight being taken and remove any jackets, outerwear and shoes. Remove any objects of significant weight (i.e. cell phones, wallet, key chains). A 5% weight loss should be reported to the medical monitor. Blood pressure will be collected while the subject is sitting/resting for at least 5 minutes.

### **5.1.5 Laboratory Tests**

All tests listed below will be performed as follows:

Screening, Baseline, Weeks 4 and 8.

All tests listed in [Table 2](#) below will be performed according to the Schedule of Visits and Assessments ([Section 1.3](#)) unless otherwise noted. The collection of specimens will be in a non-fasting state. In addition, laboratory safety tests may be performed at various unscheduled time points, if deemed necessary by the Investigator.

**Table 2: Laboratory Tests**

Hematology	Serum Chemistry

 
• Hemoglobin
 
• Hematocrit
 
• Total and differential leukocyte count
 
• Red blood cell count with indices and morphology
 
• Platelet count
 
	
 
• Blood Urea Nitrogen
 
• Bilirubin (total and direct)
 
• Alkaline phosphatase
 
• Aspartate aminotransferase
 
• Alanine aminotransferase
 
• Albumin
 
• Sodium
 
• Potassium
 
• Chloride
 
• Glucose
 
• Creatinine
 

Urinalysis	Additional Tests

 
• pH
 
• Specific gravity
 
• Protein*
 
• Glucose
 
• Ketones
 
• Bilirubin
 
• Blood*
 
• Nitrite*
 
• Urobilinogen
 
• Leukocyte esterase*
 
	
 
• Urine pregnancy test** (for females of child bearing potential only)
 
• Serum pregnancy test (hCG)***
 

\* If urinalysis is positive for protein, blood, nitrite and/or leukocyte esterase, a microscopic examination (for red blood cells, white blood cells, bacteria, casts, and epithelial cells) will be performed.

\*\* At Baseline, Weeks 4, and 8, for FOCBP only

\*\*\* At Screening, for FOCBP only

**5.1.6 Patient Health Questionnaire Depression Scale (PHQ-8)**

The 8 item PHQ-8 Assessment (see [Appendix 1](#)) will be performed in adult subjects as follows:

Screening, Baseline, Weeks 4, and 8.

Only adult subjects will complete PHQ-8 questionnaire.

A subject with a PHQ-8 score of ‘15’ or above should be referred promptly to a mental health care professional and, if currently applying IP, consideration be given to discontinuation from the IP.

PHQ-8 score is the sum of the responses for the 8 questions.

Five severity categories of depression are defined as follows:

- None – Minimal depression (0 to 4)
- Mild depression (5 to 9)
- Moderate depression (10 to 14)
- Moderately severe depression (15 to 19)
- Severe depression (20 to 24)

#### **5.1.7 Patient Health Questionnaire Depression Scale (Modified PHQ-A)**

The 8 item Modified PHQ-A Assessment (see [Appendix 2](#)) will be performed in adolescent subjects as follows:

Screening, Baseline, Weeks 4, and 8

Only adolescent subjects will complete PHQ-A questionnaire.

A subject with a Modified PHQ-A score of ‘15’ or above should be referred promptly to a mental health care professional and, if currently applying IP, consideration be given to discontinuation from the IP.

Modified PHQ-A score is the sum of the responses for the 8 questions.

Five severity categories of depression are defined as follows:

- None – Minimal depression (0 to 4)
- Mild depression (5 to 9)
- Moderate depression (10 to 14)
- Moderately severe depression (15 to 19)
- Severe depression (20 to 24)

#### **5.1.8 Columbia-Suicide Severity Rating Scale (C-SSRS)**

C-SSRS Assessments will be performed as follows:

Screening, Baseline, Weeks 4, and 8.

The administration schedule of the C-SSRS will be:

- The Baseline-Screening version ([Appendix 3](#)) will be used at Screening to provide a pre-treatment assessment baseline.
- On all subsequent visits, the Since Last Visit version ([Appendix 4](#)) will be used.
- If a subject has a score greater than 0 in suicidal ideation at Screening or Baseline, this is important and may indicate the need for mental health intervention. The investigator should not enroll the subject in the study.
- Any score greater than 0 in the suicidal ideation score is important and may indicate the need for mental health intervention and consideration be given to discontinuation from the IP. This should result in prompt referral to a mental health professional and/or possibly the emergency room. The Medical Monitor should be contacted.

The trained administrator will conduct the C-SSRS. The C-SSRS administrator will be trained via the C-SSRS training video. A training certificate for the administrator(s) will be on file in the trial master file at the site

The Investigator must review the completed C-SSRS. A qualified mental health care provider must be available, immediately if needed, to refer the subject for further evaluation.

#### 5.1.9 Local Tolerability Assessments

The Investigator Local Tolerability Assessment will be an overall assessment of local tolerability and performed as follows:

Baseline, Weeks 4, and 8

Application site reactions will be graded at the timepoints outlined in the Schedule of Visits and Assessments ([Section 1.3](#)). Irritation reactions are graded using the scale detailed in the following section ([Berger 1982](#)). **Reactions at the site of product application, which may occur post-Baseline, should be differentiated from the preexisting inflammation associated with the subject's psoriasis.**

The investigator assessments will be conducted by the investigator prior to IP application in the clinic for applicable visits.

#### Dermal Response

- 0 = no evidence of irritation
- 1 = minimal erythema, barely perceptible
- 2 = definite erythema, readily visible; minimal edema or minimal papular response
- 3 = erythema and papules
- 4 = definite edema
- 5 = erythema, edema, and papules

6 = vesicular eruption

7 = strong reaction spreading beyond application site

#### Other Effects

A = slight glazed appearance

B = marked glazing

C = glazing with peeling and cracking

D = glazing with fissures

E = film of dried serous exudates

F = small petechial erosions and/or scabs

G = no other effects

The Subject Local Tolerability Assessment will be an overall assessment of local tolerability and performed as follows:

Baseline, Weeks 4, and 8

The assessment will be administered by the site 10 to 15 minutes after IP application in the clinic at Baseline and Week 4, and a recall assessment at Week 8.

Grade	Sensation Following Drug Application
0 (none)	No sensation
1 (mild)	Slight warm, tingling sensation; not really bothersome
2 (moderate)	Definite warm, tingling sensation that is somewhat bothersome
3 (severe)	Hot, tingling/stinging sensation that has caused definite discomfort

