- e Local Tolerability Assessments: the Investigator local tolerability assessment of skin irritation (Berger and Bowman skin irritation score) should be performed prior to the investigational product application at Day 0, Weeks 4 and 8. **Note for investigator tolerability assessments: reactions at the site of product application, which may occur post-Baseline, should be differentiated from the preexisting inflammation associated with the subject's Psoriasis.** Subjects will perform the local tolerability 10-15 minutes post-IP application at Day 0 and Week 4, and recall assessment at Week 8 for the subject's '0-3' burning/stinging assessment.
- f Adolescents and adults will complete the C-SSRS. Adults will complete the PHQ-8. Adolescents will complete a modified version of the PHQ-A (PHQ-9 modified for Adolescents).
- g At selected sites, medical photography will be obtained for target lesions. All efforts will be made to de-identify the subjects. Subjects who are unwilling to participate in the medical photography will be allowed to opt out of this procedure.
- h A pregnancy test will be administered to all females of child-bearing potential. A serum pregnancy test will be performed at the Screening visit only. A urine pregnancy test will be performed at Day 0, Week 4, and Week 8. A negative result is required for continued participation in the study, and results must be available prior to dispensing of the IP at each visit.
- i PK draws will be collected at Days 0, Weeks 4 and 8 pre-dose (within 1 hour) for all subjects. Serial PK will be obtained in a subset of approximately 15 subjects on Days 0 and 28 at 1, 2, 4, 6 (all  $\pm$  20 min), and 24 hours ( $\pm$  2 hours) post-dose
- j Subjects to apply assigned IP in clinic at Day 0, Weeks 2 and 4.
- k Kits will be dispensed based on %BSA affected. See IP Handling Manual for details.
- l The entire kit should be weighed and recorded at every visit. See IP Handling Manual for details.
- m Compliance calculation is described in the IP Handling Manual
- n Any emergent AEs will be followed in the clinic for up to one month at the Investigator's discretion until resolved or otherwise judged as clinically stable.

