9.2. Local Tolerability Assessments

The investigator's assessment of the application site reaction will be summarized by study visit using both categorical methods (number and percentage of subjects with each score) as well as continuous methods (e.g., mean, median). Categorical summaries will be provided for dermal response as well as other effects. No inferential statistical tests will be performed.

The subject's assessment of the application site reaction will be summarized similarly.

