(Same shell as Table 14.3.3.1)

Table 14.3.3.3
Listing of Deaths
Safety Population

(Same shell as Table 14.3.3.1)

Table 14.3.5.1.1
Summary of Clinical Chemistry Laboratory Results by Study Visit
Safety Population

Parameter: XXXXXXXX (unit)	Roflumilast Foam 0.3%		Vehicle		Overall	
	Observed	Change	Observed	Change	Observed	Change
Baseline						
n	XX		XX		XX	
Mean (SD)	XX.X (XX.XX)		XX.X (XX.XX)		XX.X (XX.XX)	
Median	XX.X		XX.X		XX.X	
Min, Max	XX, XX		XX, XX		XX, XX	
Week 4						
n	XX	XX	XX	XX	XX	XX
Mean (SD)	XX.X (XX.XX)	XX.X (XX.XX)	XX.X (XX.XX)	XX.X (XX.XX)	XX.X (XX.XX)	XX.X (XX.XX)
Median	XX.X	XX.X	XX.X	XX.X	XX.X	XX.X
Min, Max	XX, XX	XX, XX	XX, XX	XX, XX	XX, XX	XX, XX

Repeat for Week 8. Continue for other parameters. Sort alphabetically by parameter.

Note: Subjects are summarized by treatment received and overall. Baseline is the last non-missing measurement taken before the first application of study drug.
Reference Listing: 16.2.8.1.1

Table 14.3.5.1.2
Shift from Baseline in Clinical Chemistry Laboratory Results by Study Visit
Safety Population

Study Visit	Post-Baseline Grade	Baseline Grade										Total	
		Roflumilast Foam 0.3% (N=XX)					Vehicle (N=XX)						
		Missing	Low	Normal	High	Total	Missing	Low	Normal	High	Total		
Week 4	Missing	XX (XX.X%)	XX (XX.X%)	XX (XX.X%)	XX (XX.X%)	XX (XX.X%)	XX (XX.X%)	XX (XX.X%)	XX (XX.X%)	XX (XX.X%)	XX (XX.X%)	XX (XX.X%)	XX (XX.X%)
	Low	XX (XX.X%)	XX (XX.X%)	XX (XX.X%)	XX (XX.X%)	XX (XX.X%)	XX (XX.X%)	XX (XX.X%)	XX (XX.X%)	XX (XX.X%)	XX (XX.X%)	XX (XX.X%)	XX (XX.X%)
	Normal	XX (XX.X%)	XX (XX.X%)	XX (XX.X%)	XX (XX.X%)	XX (XX.X%)	XX (XX.X%)	XX (XX.X%)	XX (XX.X%)	XX (XX.X%)	XX (XX.X%)	XX (XX.X%)	XX (XX.X%)
	High	XX (XX.X%)	XX (XX.X%)	XX (XX.X%)	XX (XX.X%)	XX (XX.X%)	XX (XX.X%)	XX (XX.X%)	XX (XX.X%)	XX (XX.X%)	XX (XX.X%)	XX (XX.X%)	XX (XX.X%)
Week 8	Missing	XX (XX.X%)	XX (XX.X%)	XX (XX.X%)	XX (XX.X%)	XX (XX.X%)	XX (XX.X%)	XX (XX.X%)	XX (XX.X%)	XX (XX.X%)	XX (XX.X%)	XX (XX.X%)	XX (XX.X%)
	Low	XX (XX.X%)	XX (XX.X%)	XX (XX.X%)	XX (XX.X%)	XX (XX.X%)	XX (XX.X%)	XX (XX.X%)	XX (XX.X%)	XX (XX.X%)	XX (XX.X%)	XX (XX.X%)	XX (XX.X%)
	Normal	XX (XX.X%)	XX (XX.X%)	XX (XX.X%)	XX (XX.X%)	XX (XX.X%)	XX (XX.X%)	XX (XX.X%)	XX (XX.X%)	XX (XX.X%)	XX (XX.X%)	XX (XX.X%)	XX (XX.X%)
	High	XX (XX.X%)	XX (XX.X%)	XX (XX.X%)	XX (XX.X%)	XX (XX.X%)	XX (XX.X%)	XX (XX.X%)	XX (XX.X%)	XX (XX.X%)	XX (XX.X%)	XX (XX.X%)	XX (XX.X%)

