A = Slight glazed appearance	XX (XX.X%)	XX (XX.X%)	XX (XX.X%)
B = Marked glazing	XX (XX.X%)	XX (XX.X%)	XX (XX.X%)
C = Glazing with peeling and cracking	XX (XX.X%)	XX (XX.X%)	XX (XX.X%)
D = Glazing with fissures	XX (XX.X%)	XX (XX.X%)	XX (XX.X%)
E = Film of dried serous exudates	XX (XX.X%)	XX (XX.X%)	XX (XX.X%)
F = Small petechial erosions and/or scabs	XX (XX.X%)	XX (XX.X%)	XX (XX.X%)
G = No other effects	XX (XX.X%)	XX (XX.X%)	XX (XX.X%)
Week 4			
A = Slight glazed appearance	XX (XX.X%)	XX (XX.X%)	XX (XX.X%)
B = Marked glazing	XX (XX.X%)	XX (XX.X%)	XX (XX.X%)
C = Glazing with peeling and cracking	XX (XX.X%)	XX (XX.X%)	XX (XX.X%)
D = Glazing with fissures	XX (XX.X%)	XX (XX.X%)	XX (XX.X%)
E = Film of dried serous exudates	XX (XX.X%)	XX (XX.X%)	XX (XX.X%)
F = Small petechial erosions and/or scabs	XX (XX.X%)	XX (XX.X%)	XX (XX.X%)
G = No other effects	XX (XX.X%)	XX (XX.X%)	XX (XX.X%)

Repeat for Week 8

Abbreviation: IP = investigational product.

Note: Percentages are n/Number of subjects in the Safety Population within treatment received and overall*100. Baseline is the last non-missing measurement taken before the first application of study drug. These assessments should be done 10 - 15 minutes after the application of IP in the study site. Subjects not meeting this condition on baseline visit are completely removed from the table summary.

Reference Listing: 16.2.9.1

Table 14.3.6.3.1
Summary of Subject Local Tolerability Assessment by Study Visit
Safety Population

(Same shell as Table 14.3.5.1.1; Reference Listing: 16.2.9.2; Repeat for Week 4, Week 8; add "IP = investigational product" to abbreviations; Add this line at the end in note footnote – "Lower scores indicate no sensation while higher scores indicate worsening/severe sensation. These assessments should be done 10 - 15 minutes after the application of IP in the study site. Subjects not meeting this condition on baseline visit are completely removed from the table summary." Change baseline definition to "Baseline for subject local tolerability assessment is the last non-missing measurement taken on the day of first application of study drug.")

Table 14.3.6.3.2
Summary of Subject Local Tolerability Assessment by Study Visit
Categorical Results
Safety Population

Study Visit Category	Roflumilast Foam 0.3% (N=XX)	Vehicle (N=XX)	Overall (N=XX)
Baseline			
0 = None (no sensation)	XX (XX.X%)	XX (XX.X%)	XX (XX.X%)
1 = Mild (slight warm, tingling sensation)	XX (XX.X%)	XX (XX.X%)	XX (XX.X%)

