2 = Moderate (definite warm, tingling sensation)	XX (XX.X%)	XX (XX.X%)	XX (XX.X%)
3 = Severe (hot, tingling/stinging sensation)	XX (XX.X%)	XX (XX.X%)	XX (XX.X%)
Week 4			
0 = None (no sensation)	XX (XX.X%)	XX (XX.X%)	XX (XX.X%)
1 = Mild (slight warm, tingling sensation)	XX (XX.X%)	XX (XX.X%)	XX (XX.X%)
2 = Moderate (definite warm, tingling sensation)	XX (XX.X%)	XX (XX.X%)	XX (XX.X%)
3 = Severe (hot, tingling/stinging sensation)	XX (XX.X%)	XX (XX.X%)	XX (XX.X%)

Repeat for Week 8

Abbreviation: IP = investigational product.

Note: Percentages are n/Number of subjects in the Safety Population within treatment received and overall*100. Baseline for subject local tolerability assessment is the last non-missing measurement taken on the day of first application of study drug. These assessments should be done 10 - 15 minutes after the application of IP in the study site. Subjects not meeting this condition on baseline visit are completely removed from the table summary.
Reference Listing: 16.2.9.2

Table 14.3.6.4.1
Summary of Vital Signs by Study Visit
Safety Population

(Same shell as Table 14.3.5.1.1; visits include Baseline, Week 2, Week 4, Week 8, Week 9; parameters include Temperature (°C), Heart Rate (bpm), Systolic Blood Pressure (mmHg), Diastolic Blood Pressure (mmHg), Height (cm), Weight (kg), and BMI (kg/m^2) [1], where [1] goes to "[1] Body Mass Index (BMI) = weight (kg) / [height (m)]²."; Reference Listings: 16.2.9.3.1, 16.2.9.4.2)

Table 14.3.6.4.2
 Shift from Baseline in Weight by Study Visit
 Safety Population

Study Visit Category	Roflumilast Foam 0.3% (N=XX)	Vehicle (N=XX)	Overall (N=XX)
Week 2			
Weight Loss \geq 10%	XX (XX.X%)	XX (XX.X%)	XX (XX.X%)
Weight Gain \geq 10%	XX (XX.X%)	XX (XX.X%)	XX (XX.X%)
Weight Loss \geq 5%	XX (XX.X%)	XX (XX.X%)	XX (XX.X%)
Weight Gain \geq 5%	XX (XX.X%)	XX (XX.X%)	XX (XX.X%)
Week 4			
Weight Loss \geq 10%	XX (XX.X%)	XX (XX.X%)	XX (XX.X%)
Weight Gain \geq 10%	XX (XX.X%)	XX (XX.X%)	XX (XX.X%)
Weight Loss \geq 5%	XX (XX.X%)	XX (XX.X%)	XX (XX.X%)
Weight Gain \geq 5%	XX (XX.X%)	XX (XX.X%)	XX (XX.X%)
Week 8			
Weight Loss \geq 10%	XX (XX.X%)	XX (XX.X%)	XX (XX.X%)
Weight Gain \geq 10%	XX (XX.X%)	XX (XX.X%)	XX (XX.X%)
Weight Loss \geq 5%	XX (XX.X%)	XX (XX.X%)	XX (XX.X%)
Weight Gain \geq 5%	XX (XX.X%)	XX (XX.X%)	XX (XX.X%)
Continue for Week 9			

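### SAP Table 14.3.6.3.1 plans a Week 8 change in the subject's burning/stinging score that subtracts an immediate post-dose rating from a recall rating, and the timing footnote on both subject tables does not fit Week 8 (minor)

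*Protocol*

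**What the plan says.** Protocol 5.1.9 sets the timing of the subject's rating: "10 to 15 minutes after IP application in the clinic at Baseline and Week 4, and a recall assessment at Week 8". Footnote e of the schedule in Protocol 1.3 agrees, with a "recall assessment at Week 8 for the subject's '0-3' burning/stinging assessment", and the SAP repeats that footnote under its own Table 1. Footnote j of the protocol schedule places the supervised doses: "Subjects to apply assigned IP in clinic at Day 0, Weeks 2 and 4". Week 8 is not among them.

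SAP 9.2 describes a by-visit summary of the investigator's score, categorical and continuous, and then adds: "The subject's assessment of the application site reaction will be summarized similarly". It does not set the recall visit apart. For the continuous table, 14.3.6.3.1, the shell instruction is "Same shell as Table 14.3.5.1.1; Reference Listing: 16.2.9.2; Repeat for Week 4, Week 8". Table 14.3.6.3.2 lists counts and percentages per grade at Baseline, Week 4 and Week 8. Both tables carry the note "These assessments should be done 10 - 15 minutes after the application of IP in the study site", with no visit named.

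**The concern.** A rating made minutes after a supervised dose captures the sensation from that dose. A recall rating captures what the subject remembers of earlier home applications, and neither document gives the period to be recalled. The two can differ even if the skin reacts identically. A table that sets them in one series, takes a change score across them and notes one timing for all visits invites the reader to see a Week 8 shift as tolerability altering with longer use. The note would also give the study report the wrong account of how the Week 8 ratings were obtained.

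**Working it through.** The documents give no figure to reproduce. The check is to trace the shells and compare them with the schedule.

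**Step 1: rating method by visit** (Protocol 5.1.9; Protocol 1.3 footnotes e and j; SAP Table 1 footnote e).

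| Visit | Dose applied in clinic | Subject rating |
|---|---|---|
| Baseline / Day 0 | Yes | Immediate |
| Week 4 | Yes | Immediate |
| Week 8 | No | Recall |

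The protocol and the SAP agree on the rating method at every row.

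**Step 2: is a Week 8 change really planned?** The SAP 9.2 text does not mention one. Table 14.3.6.3.1, however, takes its layout from Table 14.3.5.1.1, the clinical chemistry summary. That shell has Observed and Change columns at Week 4 and then instructs "Repeat for Week 8. Continue for other parameters. Sort alphabetically by parameter". SAP 6.1.1 makes a special provision so that this score has a baseline: the post-dose value on the day of first application is accepted. SAP 6.1.7 defines change as the current value minus baseline. The Week 8 change column is therefore real, but it exists in Table 14.3.6.3.1 only. Table 14.3.6.3.2 has no change column.

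**Step 3: what the change scores contain.** Write I for an immediate rating and R for a recall rating.

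- Week 4 change = I(4) − I(0): the same method on both sides.
- Week 8 change = R(8) − I(0): different methods.
- Reading Week 8 against Week 4 gives R(8) − I(4) = [I(8) − I(4)] + [R(8) − I(8)].

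The first bracket is the effect of time on treatment; the second is the effect of the rating method. I(8) is never collected, so the two brackets cannot be separated.

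**Step 4: the footnote.** Its timing matches Baseline and Week 4 and disagrees with the protocol for Week 8. The SAP is not uniform here: the note to Listing 16.2.9.2 attaches the 10 to 15 minute timing to the baseline visit only.

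**Step 5: could Week 8 records be lost?** The removal rule that follows the footnote looks at the baseline visit only, so by itself it drops no Week 8 record. SAP 6.1.1 separately excludes tolerability records not done according to protocol Section 5.1.8. In the supplied protocol that section is the C-SSRS; local tolerability is 5.1.9. A programmer who finds nothing relevant at 5.1.8 and falls back on the footnote could treat valid Week 8 recall ratings as off-protocol.

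**The case against.** The case for leaving the plan alone has several parts.

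- **Nothing is tested.** SAP 9.2 says of local tolerability: "No inferential statistical tests will be performed". No trend test and no Week 8 minus Week 4 contrast is planned. This stands. A reader might infer that the plan analyses the three visits as a trend, but the SAP describes only a by-visit summary.
- **The arms are rated alike.** Both use the same method at each visit, and the tables already show them side by side. This stands, and it matters most for severity. A reader might infer that the safety comparison of active foam with vehicle is compromised; it is not.
- **The footnote says what should be done, not what was done,** and the sentence after it acts as a baseline filter. This is partly right. The note is loosely worded rather than a false report of data, but as written it covers all visits and is wrong for Week 8.
- **The method switch is already disclosed** in the protocol section and in both schedules. That is true, but the tables will be read without those pages, and neither table labels Week 8.
- **The recall period may be given in data collection forms** that the SAP cites and that are not supplied. That is possible. A defined recall period would still not make the two methods the same.
- **Tolerability does not rest on this score alone.** The investigator's score is taken before application at Baseline, Week 4 and Week 8 under one method, and adverse events are collected throughout. This stands.

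**Conclusion.** The point holds, at minor severity. Followed literally, the shells produce one change score, the Week 8 change in Table 14.3.6.3.1, that mixes two measurements, and two tables whose timing note disagrees with the protocol for one of their three visits. What cannot be interpreted is the within-arm Week 8 change and any reading of Week 4 against Week 8.

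A stronger inference would be that any Week 8 shift is produced by the change of method. The documents do not support that. A shift could come from the method, from a real change in tolerability or from both; the table cannot tell which. No sample size, power, error rate, analysis population or efficacy result is affected.

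The conclusion assumes that visits run as scheduled: clinic doses at Day 0 and Week 4, and none at Week 8. SAP 6.2 allows this rating to be collected remotely during COVID-19 disruption, so some individual records may depart from that pattern.

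**What to change.** Four edits to the SAP:

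1. In Tables 14.3.6.3.1 and 14.3.6.3.2, label the Week 8 rows as recall, and state the recall period if the data collection forms define one.
2. In Table 14.3.6.3.1, omit the Week 8 change score and keep the Week 8 observed values.
3. In both footnotes, limit the 10 to 15 minute timing to Baseline and Week 4, and say that Week 8 is a recall rating with no clinic dose.
4. In SAP 6.1.1, change the reference from protocol Section 5.1.8 to 5.1.9, so that Week 8 recall ratings made as the protocol intends are kept.

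The cost is two table shells, their shared footnote and one cross-reference. No data collection changes. A separate block for Week 8 would also work but is not needed, and the present layout already allows the arms to be compared within each visit.
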